Patients who are re-challenged with inotuzumab or PEG-asparaginase after receiving treatment for hyperbilirubinemia may continue levocarnitine and vitamin B capsules by mouth at the discretion of the treating physician. If hyperbilirubinemia (Tbili >3 xULN) occurs, patients should receive levocarnitine and vitamin B complex starting at dose level 1 and escalate to a maximum of 150 mg/kg/day according to the recommendations above. Patients will remain on study for 30 days after their last dose of either PEG-asparaginase or inotuzumab.

Intravenous levocarnitine will be administered as an IV push over 2-3 minutes per standard of care, in accordance with MD Anderson Cancer Center IV push guidelines. Levocarnitine oral solution may be dissolved in drink or other liquid food. Oral tablets and oral solution should be administered during or following a meal. Oral solution should be consumed slowly to maximize tolerance. Missed or vomited doses of the oral tablets or solution will not be made up.

Patients will receive vitamin B complex capsules composed of: thiamine (B1) 3 mg; riboflavin (B2) 3mg; niacin (B3) 20 mg; pyridoxine HCl (B6) 0.5 mg; cyanocobalamin (B12) 1 mcg; pantothenic acid 5 mg per capsule while inpatient. Patients may receive any commercially available vitamin B complex product while outpatient even if the composition differs from what is described above. Missed or vomited doses will not be made up.

Table 1. Levocarnitine dose levels:

| Dose level | IV levocarnitine dose |
|------------|-------------------------------------|
| 1 | 50 mg/kg/day divided every 6 hours |
| 2 | 100 mg/kg/day divided every 6 hours |
| 3 | 150 mg/kg/day divided every 6 hours |

6.1.1 Compatibility:

Levocarnitine injection solution is compatible and stable when mixed in parenteral solutions of Sodium Chloride 0.9% or Lactated Ringer's in concentrations ranging from 250 mg/500 mL (0.5 mg/mL) to 4200 mg/500 mL (8.0 mg/mL)

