11.0 STATISTICAL CONSIDERATIONS

This is an open label phase II study to evaluate the efficacy of levocarnitine and vitamin B complex for the treatment of hyperbilirubinemia ($Tbili > 3 \times ULN$) in adult patients with ALL treated with PEG-asparaginase or inotuzumab ozogamicin.

Two cohorts of patients will be enrolled in the study, patients who were previously treated with PEG-asparaginase and patients who were previously treated with inotuzumab. Evaluation for two cohorts of patients will be separated. Up to 39 patients will be enrolled for each cohort. Total sample size is up to 78.

The primary efficacy endpoint is response, which is defined as bilirubin normalization (TBili \leq 1.5 x ULN) or at least a 50% reduction in peak bilirubin level in 11 days for patients previously treated with PEG-asparaginase and bilirubin normalization (TBili \leq 1.5 x ULN) or at least a 50% reduction in peak bilirubin level in 7 days for patients previously treated with inotuzumab after initiation of the study treatment. All patients who receive at least 1 dose of levocarnitine will be assessed for safety. Patients must receive at least 5 consecutive days of levocarnitine to be considered evaluable for response.

Our retrospective data suggested that without any treatment the median time to bilirubin normalization (TBili \leq 1.5 x ULN) or at least a 50% reduction in peak bilirubin level was 21 days for patients previously treated with PEG-asparaginase, and the median time to achieve hyperbilirubinemia normalization (TBili \leq 1.5 x ULN) or at least a 50% reduction in peak bilirubin level was 14 days for patients previously treated with inotuzumab. Assuming that the time to normalization follows exponential distributions, then estimated failure rate (no normalization of grade \geq 3 hyperbilirubinemia or less than 50% reduction in peak total bilirubin) would be 70% at day 11 for patients previously treated with PEG-asparaginase and at day 7 for patients previously treated with inotuzumab, respectively. This corresponding to a response rate of 30%.

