With the proposed study treatment, it is expected that the median time to achieve hyperbilirubinemia normalization or at least a 50% reduction in peak total bilirubin will be shortened to 11 days for patients previously treated with PEG-asparaginase, and to 7 days for patients previously treated with inotuzumab. That is corresponding to a 20% increase in response rate (i.e. an increase from 30% to 50%) for each of the cohort of patients.

Simon's two-stage Minimax design³² will be implemented for each cohort of patients. The null hypothesis that the true response rate is 30% will be tested against a one-sided alternative 50%. In the first stage, 19 patients will be accrued. If there are 6 or fewer responses in these 19 patients, the study will be stopped. Otherwise, 20 additional patients will be accrued for a total of 39. The null hypothesis will be rejected if 17 or more responses are observed in 39 patients. This design yields a one-sided type I error rate of 0.05 and power of 80% when the true response rate is 50%. The expected sample size is 25.7 and the probability of early stop is 66.6% under the null hypothesis.

Analysis Plan:

The primary endpoint is bilirubin normalization or at least a 50% reduction in peak total bilirubin in patients treated with levocarnitine and vitamin B complex. Response rates will be estimated along with the 95% confidence interval. Secondary endpoints include tolerability of levocarnitine and vitamin B complex and chemotherapy dose intensity. Descriptive statistics will be used to summarize secondary endpoints. The incidence rates of binary secondary endpoints will be estimated, along with the 95% confidence intervals. The duration of time to hyperbilirubinemia normalization or at least a 50% reduction in peak total bilirubin will be estimated using the Kaplan-Meier method. For exploratory purposes, the time to hyperbilirubinemia normalization or achieving at least a 50% reduction in peak total bilirubin will be compared to historical controls using the Log rank test. Competing risk analysis will be considered in the case that patients died before bilirubin normalization or at least a 50% reduction in peak total bilirubin is achieved.

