- A persistent or significant incapacity or substantial disruption of the ability to conduct normal life functions.
- A congenital anomaly/birth defect.

Important medical events that may not result in death, be life-threatening, or require hospitalization may be considered a serious adverse drug experience when, based upon appropriate medical judgment, they may jeopardize the patient or subject and may require medical or surgical intervention to prevent one of the outcomes listed in this definition. Examples of such medical events include allergic bronchospasm requiring intensive treatment in an emergency room or at home, blood dyscrasias or convulsions that do not result in inpatient hospitalization, or the development of drug dependency or drug abuse (21 CFR 312.32).

- Important medical events as defined above, may also be considered serious adverse events. Any important medical event can and should be reported as an SAE if deemed appropriate by the Principal Investigator or the IND Sponsor, IND Office.
- All events occurring during the conduct of a protocol and meeting the definition of a SAE must be reported to the IRB in accordance with the timeframes and procedures outlined in "The University of Texas M. D. Anderson Cancer Center Institutional Review Board Policy for Investigators on Reporting Unanticipated Adverse Events for Drugs and Devices". Unless stated otherwise in the protocol, all SAEs, expected or unexpected, must be reported to the IND Office, regardless of attribution (within 5 working days of knowledge of the event).
- **All life-threatening or fatal events**, that are unexpected, and related to the study drug, must have a written report submitted within **24 hours** (next working day) of knowledge of the event to the Safety Project Manager in the IND Office.
- Unless otherwise noted, the electronic SAE application (eSAE) will be utilized for safety reporting to the IND Office and MDACC IRB.
- Serious adverse events will be captured from the time of the first protocol-specific intervention, until 30 days after the last dose of drug, unless the participant withdraws consent. Serious adverse events must be followed until clinical recovery is complete and laboratory tests have returned to baseline, progression of the event has stabilized, or there has been acceptable resolution of the event.

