- Additionally, any serious adverse events that occur after the 30 day time period that are related to the study treatment must be reported to the IND Office. This may include the development of a secondary malignancy.

Reporting to FDA:

- Serious adverse events will be forwarded to FDA by the IND Sponsor (Safety Project Manager IND Office) according to 21 CFR 312.32.

It is the responsibility of the PI and the research teams to ensure serious adverse events are reported according to the Code of Federal Regulations, Good Clinical Practices, the protocol guidelines, the sponsor's guidelines, and Institutional Review Board policy.

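### Does ending on-study time 30 days after the last PEG-asparaginase or inotuzumab dose cut short safety capture or time-to-response follow-up?

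*Combined protocol and SAP*

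**What the plan says.** The only statement of on-study duration is in section 6.1 (General): "Patients will remain on study for 30 days after their last dose of either PEG-asparaginase or inotuzumab". It ends a paragraph that opens "Patients who are re-challenged with inotuzumab or PEG-asparaginase after receiving treatment for hyperbilirubinemia may continue levocarnitine and vitamin B capsules by mouth". The sentence immediately before it deals with hyperbilirubinemia that returns in those patients. The duration sentence itself is not restricted to them.

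Two other periods use different anchors.

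- **Response.** Sections 9.0 and 11.0 (Statistical Considerations) count 11 days (PEG-asparaginase cohort) or 7 days (inotuzumab cohort); section 11.0 starts the count at study treatment.
- **SAEs.** Section 11.0 (Reporting Requirements) states: "Serious adverse events will be captured from the time of the first protocol-specific intervention, until 30 days after the last dose of drug". It adds that "any serious adverse events that occur after the 30 day time period that are related to the study treatment must be reported". The drug is not named in the first of these. The surrounding text speaks of study drug and study treatment, so levocarnitine with vitamin B is the natural reading.

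For time to response, the Analysis Plan states: "The duration of time to hyperbilirubinemia normalization or at least a 50% reduction in peak total bilirubin will be estimated using the Kaplan-Meier method". As an exploratory step, that time "will be compared to historical controls using the Log rank test". No follow-up length or censoring date is given for patients without a response.

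**The concern.** The duration rule follows the drug that caused the toxicity and not the drug under test. A patient starts levocarnitine some days after the last PEG-asparaginase or inotuzumab dose and, under section 6.1, may stay on it past the response window if there is no response. If the rule is a cap for everyone, such a patient could be off study while SAE capture is running, and possibly while still being treated. The section 8.0 laboratory tests would then no longer be required, and time to response would be censored at a point that differs between patients and depends on d, which the protocol does not control. A Kaplan-Meier curve that stops before its median, set against historical medians of 21 and 14 days, would be of little use. In the extreme, the primary window itself could be truncated.

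**Working it through.** **The plan's own figures.** The planning passage begins "Assuming that the time to normalization follows exponential distributions". With response by day t equal to 1 - 2^(-t/median), the historical medians give 1 - 2^(-11/21) = 30.4% (PEG-asparaginase) and 1 - 2^(-7/14) = 29.3% (inotuzumab), in line with the stated 30%. The expected median "will be shortened to 11 days for patients previously treated with PEG-asparaginase, and to 7 days for patients previously treated with inotuzumab", which gives 50% in each cohort. Exact binomial enumeration of the two-stage rule (stop at 6 or fewer of 19; reject at 17 or more of 39) gives type I error 0.0455, power 0.8036, expected sample size 25.69 and early-stop probability 0.6655. The plan states 0.05, 80%, 25.7 and 66.6%. None of these depends on the on-study rule.

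**Inputs for the worst reading.** Assume the sentence applies to all patients, is a cap, and no later causative dose is given. Count days from the last causative dose and let levocarnitine start on day d. The documents give no value for d; 0, 7, 14 and 21 are assumptions. Section 11.0 (Statistical Considerations) requires five days of levocarnitine in a row for a patient to be evaluable.

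**Formulas.**

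- On-study follow-up from treatment start: 30 - d.
- SAE capture, taking the unnamed drug as study drug: with five days of treatment the last dose is on day d + 4, capture ends on day d + 34, and the excess over day 30 is d + 4. Longer treatment makes it longer.
- Share still without a response when on-study time ends: 2^(-(30 - d)/median).
- Response-window days lost: max(0, d - 19) for PEG-asparaginase (30 - 11 = 19) and max(0, d - 23) for inotuzumab (30 - 7 = 23).

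| | d = 0 | d = 7 | d = 14 | d = 21 |
|---|---|---|---|---|
| On-study follow-up (days) | 30 | 23 | 16 | 9 |
| SAE capture beyond on-study time (days, at least) | 4 | 11 | 18 | 25 |
| No response, PEG, expected median 11 | 15.1% | 23.5% | 36.5% | 56.7% |
| No response, inotuzumab, expected median 7 | 5.1% | 10.3% | 20.5% | 41.0% |
| No response, PEG, historical median 21 | 37.1% | 46.8% | 59.0% | 74.3% |
| No response, inotuzumab, historical median 14 | 22.6% | 32.0% | 45.3% | 64.0% |
| Window days lost, PEG / inotuzumab | 0 / 0 | 0 / 0 | 0 / 0 | 2 / 0 |

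Follow-up reaches the historical median if d is at most 30 - 21 = 9 (PEG-asparaginase) or 30 - 14 = 16 (inotuzumab). It reaches the expected median if d is at most 19 or 23.

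**What the text supports.** Each premise is open to doubt.

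1. *Scope.* The sentence's position favours re-challenged patients. On that reading none of the table applies to patients who are not re-challenged; what remains is that no end date is written for them.
2. *Cap or minimum.* Remaining on study for 30 days can be a minimum. Section 6.1 does not say that patients come off study or that data collection stops then, and section 8.0 gives its tests no end date. Section 6.1 also lets non-responders continue protocol medication with no calendar limit, which fits poorly with having already left the study.
3. *No later dose.* Section 5.0 enrols patients in the course of PEG-asparaginase or inotuzumab treatment, and every further dose restarts the 30 days.
4. *SAE capture.* Its end date is set independently of on-study status, and related events remain reportable afterwards. If the unnamed drug meant the causative drug, the two end dates would coincide.

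**The case for a change.** The strongest case for a change is that each reading leaves something unsaid. If the sentence covers everyone, on-study time and SAE capture do not line up. If it covers only re-challenged patients, nobody else has a stated end of study. If the unnamed drug is the causative one, routine SAE capture could finish while levocarnitine continues. Section 2.1 itself says that PEG-asparaginase toxicity can persist long after a dose, so late treatment is not fanciful, and settling the wording costs little.

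The ambiguity stands; the harm does not. Different periods may properly have different anchors, and following patients from the last PEG-asparaginase or inotuzumab dose suits the dose-intensity objective in section 1.2. A patient still on levocarnitine will usually have bilirubin values, because escalation and stopping in section 6.1 depend on them. Section 8.0 already leaves outpatient fractionated bilirubin to the physician, so the required outpatient test at issue is the weekly metabolic panel. Shorter follow-up is ordinary administrative censoring, which Kaplan-Meier handles if d is unrelated to time to response; nothing in the documents shows that it is related.

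The obvious amendment would run follow-up to the latest of three dates: 30 days after the last study dose, the end of the response window, and 30 days after the last causative dose. The second can never bind, since the first always falls later than day 11 or day 7. The first could extend the weekly panel for some patients, with no gain for the primary result.

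**Conclusion.** No change to the plan is needed. The wording leaves scope, cap or minimum, and the censoring date unstated, but followed as written it leaves the primary response definition, type I error, power, sample size and SAE capture sound. The losses in the table need four things together: the all-patients reading, the cap reading, no later causative dose, and values of d that the documents do not supply. Even then the primary window is untouched up to d = 19 days (PEG-asparaginase) or 23 days (inotuzumab), and d = 21 costs 2 days in one cohort and none in the other. What could shrink is follow-up for a descriptive Kaplan-Meier curve and an exploratory log-rank test. An analyst would censor patients without a response at their last bilirubin measurement and report the follow-up achieved, which is adequate for those purposes. The conclusion assumes that bilirubin continues to be recorded while levocarnitine is given, as the section 6.1 treatment rules imply, and that d is unrelated to time to response.

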7.0 Pretreatment evaluation

- 7.1 Informed consent
- 7.2 Baseline comprehensive metabolic panel (CMP)
- 7.3 Concomitant medications within 14 days of enrollment
- 7.4 Urine or serum pregnancy test for women of childbearing potential within 7 days of initiating chemotherapy

8.0 Evaluation During Study

- 8.1 Comprehensive metabolic panel (CMP) at least weekly
- 8.2 Concomitant medications
- 8.3 Additional monitoring procedures including but not limited to CMP, fractionated bilirubin, serum albumin, diagnostic imaging, to be completed per institutional guidelines. Additional monitoring not required for study. Failure to perform this will not be considered a protocol deviation or violation.
- 8.4 Fractionated bilirubin daily while inpatient, then per treating physician discretion while outpatient.

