6.0 Treatment Plan

6.1 General

All patients will be registered with the Data Management Office PDMS/CORE system.

Treatment with levocarnitine and vitamin B complex will be initiated when total bilirubin is >3xULN. Treatment will consist of IV levocarnitine 50 mg/kg loading dose (maximum 3000 mg) followed by 50 mg/kg/day divided every 6 hours beginning 6 hours after the loading dose was administered. Levocarnitine dose may be increased by 50 mg/kg/day to a maximum of 150 mg/kg/day divided every 6 hours (maximum 3000 mg per dose) if no improvement in total bilirubin after 2 consecutive days of treatment at each dose level. See Table 1 for dosing levels. Treatment will continue until total bilirubin is \leq 1.5 x the upper limit of normal (ULN) or at least a 50% reduction in peak total bilirubin is achieved. If hyperbilirubinemia recurs (Tbili >3xULN), levocarnitine and vitamin B may be reinitiated at the previous dose level and continued until Tbili \leq 1.5 x ULN or at least a 50% reduction in peak total bilirubin is achieved. It is preferred that the patient continue to receive treatment as inpatient. If the treating physician deems patient appropriate for discharge prior to achieving a Tbili of \leq 1.5 ULN or at least a 50% reduction in peak total bilirubin, it is recommended for patient to continue IV levocarnitine as an outpatient. It is recommended for patient to continue IV levocarnitine as an outpatient at the same inpatient dosage divided twice daily (maximum 3000mg per dose). If patient is unable to continue IV levocarnitine as an outpatient, it is recommended the patient receive levocarnitine 990 mg by mouth three times daily until Tbili of \leq 1.5 ULN or at least a 50% reduction in

peak total bilirubin is achieved. Vitamin B complex 1 capsule will be administered by mouth twice daily until Tbili of \leq 1.5 ULN or at least a 50% reduction in peak total bilirubin is achieved. Patients who do not achieve a response within the timeframe of interest may continue to receive protocol medications including levocarnitine and vitamin B complex if there is clinical benefit, and deemed in best interest of the patient by the treating physician.

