9.0 Response

- 9.1. Normalization of hyperbilirubinemia ($Tbili \leq 1.5 \times ULN$) or at least 50% reduction in peak total bilirubin within 11 days in patients who received PEG-asparaginase
- 9.2. Normalization of hyperbilirubinemia ($Tbili \leq 1.5 \times ULN$) or at least 50% reduction in peak total bilirubin within 7 days in patients who received inotuzumab ozogamicin

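### No bilirubin is guaranteed at the end of the primary endpoint window (day 11 PEG, day 7 inotuzumab) for patients discharged before response

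*Combined protocol and SAP*

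**What the plan says.** Section 9.0 defines PEG response as normalization or "at least 50% reduction in peak total bilirubin within 11 days in patients who received PEG-asparaginase". The inotuzumab definition is the same with 7 days. Section 11.0 (Statistical Considerations) sets the starting point of the clock: "in 7 days for patients previously treated with inotuzumab after initiation of the study treatment".

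Section 6.1 favours hospital care ("It is preferred that the patient continue to receive treatment as inpatient") but does not require it. It provides for earlier discharge ("If the treating physician deems patient appropriate for discharge prior to achieving a Tbili of" the response threshold), recommends continued outpatient IV treatment, and allows an oral route: "If patient is unable to continue IV levocarnitine as an outpatient, it is recommended the patient receive levocarnitine 990 mg by mouth".

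Section 8.0 sets the tests. Item 8.1 is "Comprehensive metabolic panel (CMP) at least weekly". Item 8.4 is "Fractionated bilirubin daily while inpatient, then per treating physician discretion while outpatient". Item 8.3 leaves further panels and bilirubin tests to institutional guidelines and does not require them for the study. No item is tied to day 7 or day 11.

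Section 11.0 makes a patient evaluable for response after 5 consecutive days of levocarnitine. It asks for no bilirubin at the end of the window and gives no rule for a patient who lacks one.

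**The concern.** A yes/no endpoint with a fixed window needs a measurement at the end of the window. Inpatients have daily values. A patient discharged before response may have only a weekly panel on days unrelated to the start of treatment.

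If the last draw inside the window shows no response and the next one, after the window, does, nobody can tell whether the threshold was crossed in time. The patient is still evaluable and stays in the denominator. If such patients count as failures, each cohort's response rate is biased downward. Stage 1 turns on 6 versus 7 responders among 19, so one or two misplaced patients can decide whether a cohort continues. The planned Kaplan-Meier and log-rank analyses would also rest on times known only to lie between two draws.

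**Working it through.** **Inputs.** From Section 11.0: exponential time to response; PEG median 21 days (historical) and 11 days (expected on treatment); inotuzumab 14 and 7 days; null rate 30%, alternative 50%; stop if 6 or fewer of 19 respond; reject the null if 17 or more of 39 respond. From Section 8.1: at least one panel a week. Assumed: the panel includes total bilirubin (the protocol does not list its components). Not in the documents: the share f of patients who have only weekly draws.

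**Reproducing the plan.** Response by day t is 1 − 2^(−t/median).
- PEG: 1 − 2^(−11/21) = 30.4% under the null and 1 − 2^(−11/11) = 50.0% under the alternative.
- Inotuzumab: 1 − 2^(−7/14) = 29.3% and 1 − 2^(−7/7) = 50.0%.
- Exact two-stage binomial: type I error 0.0455 at 30%, power 0.8036 at 50%, early stop 66.6% and expected size 25.7 under the null. All agree with the plan. The chance of stopping at stage 1 when the true rate is 50% is 8.4%.

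**Gap in the PEG cohort.** Draws on days 7 and 14 satisfy 8.1. Under the alternative, 1 − 2^(−7/11) = 35.7% have responded by day 7, so 50.0 − 35.7 = 14.3 points fall between days 7 and 11. With weekly draws the last one in the window can fall on any day from 5 to 11. The loss for last day d is 2^(−d/11) − 0.5:

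| d | 5 | 6 | 7 | 8 | 9 | 10 | 11 |
|---|---|---|---|---|---|---|---|
| loss | 0.230 | 0.185 | 0.143 | 0.104 | 0.067 | 0.033 | 0 |

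The mean over the seven days is 0.109.

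**Gap in the inotuzumab cohort.** The last weekly draw in the window can fall on days 1 to 7. The loss is 2^(−d/7) − 0.5: zero on day 7, 0.052 on day 6, 0.110 on day 5. The mean over days 1 to 7 is 0.186.

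**Effect on the PEG design, for illustration.** Suppose a share f of all PEG patients has only weekly draws, unseen responses count as failures, 50% is the fully observed rate, and sampling is independent of time to response. The observed rate is then 0.50 − f × loss.

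| f | last draw day 7: rate, power, stage 1 stop | even spread over days 5–11: rate, power, stage 1 stop |
|---|---|---|
| 0 | 0.500, 80.4%, 8.4% | 0.500, 80.4%, 8.4% |
| 5% | 0.493, 77.9%, 9.4% | 0.495, 78.5%, 9.1% |
| 10% | 0.486, 75.3%, 10.5% | 0.489, 76.5%, 9.9% |
| 25% | 0.464, 66.4%, 14.3% | 0.473, 70.1%, 12.6% |

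**Type I error.** Under the null the points between days 7 and 11 are 2^(−7/21) − 2^(−11/21) = 0.098. At f = 10% the observed rate is 0.30 − 0.10 × 0.098 = 0.290, and the type I error falls from 0.0455 to 0.034.

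**The case against.** The strongest reply is that weekly-only sampling will be uncommon. Weekly is a minimum, inpatient care with daily bilirubin is preferred, and the Section 6.1 rules for escalating and ending treatment cannot be applied without bilirubin values. This stands as a reason to expect a small f. It does not close the gap: neither rule sets an outpatient schedule or a draw at the end of the window, and Section 10.0 foresees care by a local physician whose documentation duty covers protocol-required tests.

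Second, the power figures are hypothetical. That is right. f is not documented, and no rule says a late-seen response is a failure. The loss formula is also averaged over all PEG patients, including those who respond early; for a patient still unresponsive on day 7 the chance of responding by day 11 is 0.143/0.643 = 0.223. The table therefore does not describe the patients discharged before response. The equal weights over days 5 to 11 have no basis in the documents either, and ignore daily values before discharge.

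Third, the benchmark may share the problem. Section 11.0 says only "Our retrospective data suggested that without any treatment the median time to bilirubin normalization" and the medians; it does not describe how those patients were sampled. If the 30% and 50% rates include the same detection delay, nothing is lost. If historical sampling was sparser, a fixed draw in the trial alone would favour the trial.

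A reader might infer that the PEG cohort stands to lose 14.3 points. It does not: that is the loss if every patient's last in-window draw were on day 7. Nor do outpatients go without any required test, since 8.1 still applies. And it would be wrong to treat inotuzumab as safe because 7 days matches a weekly test: 8.1 does not start the week at the first levocarnitine dose.

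**Conclusion.** The gap is real in both cohorts. For a patient discharged before response, a compliant schedule can leave the end of the window unmeasured, and the plan does not say how that patient is classified. If late-seen responses count as failures, and the planning rates assume full observation, the bias is downward: lower power and a higher chance of stopping a working treatment at stage 1, without inflation of type I error.

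The size cannot be determined from the documents. If 10% of PEG patients had a last in-window draw on day 7, power would lie between 75.3% (rates fully observed) and 80.4% (rates already include the delay). The stated design figures are correct. This is a weakness in endpoint ascertainment that is cheap to repair, not a failure of the design.

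**What to change.** In Section 8.0, schedule the already required panel, with total bilirubin, on day 11 for PEG and day 7 for inotuzumab, counted from the first levocarnitine dose, for every treated patient not yet in response, inpatient or outpatient. The result is then protocol-required, so the documentation duties in 10.3 and 10.6 cover it when care is given elsewhere.

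In Section 9.0 or Section 11.0 (Statistical Considerations), state the tolerance allowed for that draw and how a patient without an in-window value at the end of the window is classified. Without these, a missed draw or one on day 12 brings the ambiguity back.

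The cost is protocol wording and one or at most two routine draws per patient discharged before response, with no new procedure. The trial may then be sampled more closely than the historical data; the comparison should acknowledge this and, where possible, describe how the historical patients were sampled.
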